### **12.6 Time Windows**

Data as evaluated during regular visits will be analysed in accordance to the respective visit. Time window violations will only be considered for lipid data analyses and for analyses using the PP. Visit windows will be defined in the Statistical Analysis Plan. A data review meeting will be performed prior to data base lock and it may be decided to exclude single visits from the PP analyses due to time window violation. For time to event analyses, the exact visit dates and D0 will be taken for calculating the time to event.

## 13 QUALITY CONTROL AND QUALITY ASSURANCE

### 13.1 Pre-study Documentation

Prior to enrolment of patients at a study site, specific regulatory documents must be available, such as Independent Ethics Committee (IEC)/Institutional Review Board (IRB) approval and curricula vitae of investigators and study staff. Amryt Pharmaceuticals DAC will inform the investigator which documents need to be provided according to the applicable regulatory requirements.

### 13.2 Monitoring

Amryt Pharmaceuticals DAC will appoint qualified and appropriately trained persons to monitor the study and the FU. Monitors will periodically contact the site and perform site visits in accordance with applicable regulations, GCP and Amryt Pharmaceuticals DAC approved procedures. Study objectives, study design, and enrolment rate will determine the extent, nature and frequency of site visits.

The monitor will contact the site before the start of the study to discuss the protocol and data collection procedures with the site study team members.

During site visits, the monitor will:

- Check and assess the progress of the study
- Review study data collected
- Perform source data verification
- Identify any issues and address their resolution

Aim of the site visits is to verify that:

- The data are authentic, accurate and complete
- The safety and rights of patients are being protected
- The study is conducted in accordance with the approved protocol (and any subsequent amendment), GCP and all applicable regulatory requirements

The investigator agrees to allow the monitor direct access to all relevant documents and to allocate his/her time and the time of his/her staff to the monitor to discuss findings and any relevant issues.

The study monitor will record any protocol deviations identified, including, but not limited to, patients that were enrolled even though they did not meet all eligibility criteria, patients who took concomitant medications specifically prohibited by the protocol, patients who received an incorrect dose of study medication, and patients who failed to comply with the protocol-defined dietary restrictions. The Investigator and study team members will collaborate with the study monitor to identify the reason for each protocol deviation.

At study closure, the monitor will conduct all activities as indicated in Section 13.4 *Study and Site Closure*.

### 13.3 Data Management and Processing

Amryt Pharmaceuticals DAC is responsible for data quality control. Each study site is responsible for the data documentation and for the maintenance of patient files.

### **13.3.1 Data Collection**

The investigator or an authorised delegate from the study staff will have to complete an eCRF for each patient enrolled including patients who discontinue prematurely. If a patient withdraws from the study, the reason should be noted in the eCRF if possible. If a patient is withdrawn from the study because of a treatment-limiting AE, thorough efforts should be made to clearly document the outcome.

The investigator should ensure the accuracy, completeness, legibility, and timeliness of the data reported to the sponsor in the eCRFs and in all required reports.

### **13.3.2 Data Management Procedures**

A separate '*Data Management Plan*' will detail data management vendors, systems and processes.

### **13.3.3 Data Verification Procedures**

Data will be checked systematically according to a pre-specified '*Data Validation Plan*' after they have been entered into the study database. Queries will be created for errors or missing data and clarified by the study monitor at the investigational site.

### **13.3.4 Coding**

All AEs and concomitant diseases will be coded according to MedDRA and all concomitant or previous medication based on the World Health Organization (WHO) Drug Dictionary.

### **13.3.5 Procedures for Analysis of Consistency and Medical Plausibility**

A data review meeting will be conducted as soon as all data of the study and the follow-up period has been entered into the eCRF and the database has been confirmed as 'clean'. After resolution of all remaining queries, the Statistical Analysis Plan will be finalised and the database will be locked. All changes to the data will be kept in an audit trail.

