## **12 STATISTICAL ANALYSIS**

### **12.1 Statistical Methods**

The primary efficacy analysis will be conducted once all patients have completed (or withdrawn prior to Visit 10) at Week 24±3 days (End of the Efficacy Phase). The primary efficacy analysis will include the key primary/secondary efficacy data, all safety data available up to the data cut-off date of the last patient reaching Week 24±3 days, and PK parameter analysis. The reporting of Week 24±3 days data will allow for an early submission of an application for regulatory approval of Lojuxta® in the paediatric indication. The final statistical analysis will be performed when all patients have completed the Follow-up Visit (Visit 23) at Week 108±7 days. Efficacy, safety, and exploratory data collected during both the Safety Phase and follow-up will be included.

No interim efficacy analyses for efficacy and/or futility will be performed as outlined in Section 12.3.3 *Interim Analysis*.

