## **12.3 Planned Analysis**

Full details of the planned analyses will be documented in a Statistical Analysis Plan prior to database lock. The primary estimand will be a 'treatment policy' estimand which will be defined in the Statistical Analysis Plan.

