### **12.3.3 Interim Analysis**

No interim efficacy analyses for efficacy and/or futility will be performed.

The primary efficacy analysis and final statistical analysis will be performed as described in Section 12.1 *Statistical Methods*.

An independent DSMB will periodically review the safety data as described in Section 4.3 *Data Safety Monitoring Board*.

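### Section 13.3.5 makes the statistical analysis plan final only after the Week 108 data are in and clean, yet Section 12.1 runs and reports the confirmatory primary analysis at Week 24

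*Protocol*

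**What the plan says.** Protocol Section 13.3.5 gives the only closing sequence that is tied to a point in the study. It starts with the review meeting: "A data review meeting will be conducted as soon as all data of the study and the follow-up period has been entered into the eCRF". A clean database is a further condition for that meeting. The sequence ends: "After resolution of all remaining queries, the Statistical Analysis Plan will be finalised and the database will be locked".

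Section 12.1, repeated in the synopsis, sets two analyses. For the first: "The primary efficacy analysis will be conducted once all patients have completed" Visit 10 at Week 24 or withdrawn before it. Its purpose is stated: "The reporting of Week 24±3 days data will allow for an early submission of an application for regulatory approval". The data state named there is a cut-off, attached to "all safety data available up to the data cut-off date of the last patient reaching Week 24±3 days". For the second: "The final statistical analysis will be performed when all patients have completed the Follow-up Visit (Visit 23) at Week 108±7 days".

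Section 12.3 sets a general rule for the plan: "Full details of the planned analyses will be documented in a Statistical Analysis Plan prior to database lock". It leaves the definition of the treatment-policy estimand to that plan. Section 12.6 leaves the visit windows to it as well, says that window violations count for lipid analyses, and places a data review meeting before lock. Section 12.2 leaves per-protocol exclusions to case-by-case decisions in such a meeting. Neither Section 12.3 nor Section 12.6 says which lock is meant.

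**The concern.** The two instructions cannot both be followed if the SAP is to be final before the analysis it governs. Section 12.1 puts the confirmatory analysis at Week 24. Section 13.3.5 puts the final SAP after Week 108.

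Section 12.3.3 states: "No interim efficacy analyses for efficacy and/or futility will be performed". Week 24 is therefore the first planned aggregate efficacy output, and so the natural point by which the analysis rules must be settled. Under the sequence as written, anything the protocol hands on to the SAP or to the review meeting could be decided after that output has been produced and submitted. For those items, a SAP dated after the submission could not serve as evidence that they were chosen beforehand.

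**Working it through.** **Timing.** The inputs are the scheduled weeks in the synopsis and Section 4.2.1: Efficacy Phase 24 weeks, Safety Phase 80 weeks, follow-up 4 weeks.

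- The protocol's own end point is reproduced: 24 + 80 + 4 = 108 weeks.
- Trigger of the primary analysis: the last patient's Week 24 visit (Section 12.1).
- Earliest start of the Section 13.3.5 sequence: the last patient's Week 108 contact.
- Gap: 108 − 24 = 84 weeks = 80 + 4. In months: 84 × 7 / 30.44 = 19.3.
- Effect of the visit windows (±3 days at Week 24, ±7 days at Week 108): at most 10 days either way. The shortest gap is 588 − 10 = 578 days, or 82.6 weeks.
- Data entry, cleaning, the review meeting and query resolution come on top.

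**Does any other text give an earlier date for the SAP?**

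| Place | What it offers | Does it place the SAP before Week 24? |
|---|---|---|
| 12.1 and synopsis | a Week 24 data cut-off, worded for safety data | No; no lock and no SAP step is named |
| 12.3 | SAP before lock | No; the lock is not identified |
| 12.6 | review meeting before lock | No; the lock is not identified |
| 12.2 | review meeting for per-protocol decisions | No; no date |
| 12.3.3 | refers back to 12.1 | No |
| 13.3.2 | refers data-management processes to a separate plan | No; says nothing about the SAP date |
| 13.3.5 | SAP final, then lock | No; after all follow-up data |

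**What is exposed?** The protocol already fixes the following:

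- endpoint at Week 24±3 days (4.1.1);
- full analysis set as the primary population (12.2);
- one-sample t-test, last observation carried forward (LOCF) and an MMRM sensitivity analysis (12.3.4);
- two-sided alpha of 0.05 and the order of the secondary tests (12.1.1).

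Three items remain open:

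1. *Estimand.* The strategy is named in 12.3; the detailed definition is deferred.
2. *Lipid visit windows.* The ±3 days is given, but the handling of samples outside it is deferred (12.6). If a rule sets aside a Week 24 sample taken too early or too late, the value counts as missing and Section 12.3.4 replaces it with an earlier one by LOCF. Results from unscheduled visits are also entered in the eCRF (9.6), so the rule may decide whether they count. By this route a deferred choice can reach the primary estimate.
3. *Per-protocol exclusions* of patients (12.2) and of single visits (12.6). These affect supplementary analyses only.

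The document gives no expected number of out-of-window samples or exclusions, so no bias can be calculated.

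**The case against.** The best reply is that Section 13.3.5 is a data-management paragraph describing the close-out lock. It does not say that there is only one lock. Section 12.3 carries the statistical rule, Section 12.1 recognises a Week 24 cut-off, and lock procedures may sit in the Data Management Plan that Section 13.3.2 refers to. On this view the wording was simply not adapted to a two-stage analysis. That is probably how it arose. It explains the conflict without removing it: the text speaks of the SAP and the database without qualification, and nothing in the protocol provides a Week 24 counterpart.

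A second reply is that handing details to a SAP is ordinary practice. That stands in full. The fault lies only in the stated time at which the SAP becomes final.

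A third reply is that the main analysis is already prespecified. This also stands, and it bounds the point. A reader might infer that the submitted primary analysis would lack prespecification altogether, or that its significance is in doubt. The document supports neither, because the components listed above are fixed in the protocol whatever the date of the SAP.

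A reader might also bring in the open-label design, with sites seeing local LDL-C results and LDL-C guiding escalation. That access exists whenever the SAP is signed, so it neither creates this defect nor is cured by the fix. Nor does the wording show any intention to choose rules after seeing results, and a SAP may in practice have been signed earlier. The point concerns what the protocol states.

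**Conclusion.** Wrong as written. Section 13.3.5 places finalisation of the SAP about 84 weeks, or 19 months, after the last patient's Week 24 visit, and so after the confirmatory result is known and reported. The interval rests on the nominal schedule and assumes that the last patient to reach Week 24 also completes follow-up; the visit windows move it by at most 10 days.

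The consequence is limited to the three deferred items. Of these, the handling of window violations is the one with a clear route to the primary estimate, while the per-protocol decisions touch supplementary analyses only. What is at risk is the evidence that those items were settled in advance. The conflict in wording is certain; its effect on the estimate is unknown and may be nil. The correction is still worth making, because it is cheap and protects the analysis meant for submission.

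**What to change.** - In Section 13.3.5, say that the described sequence applies to the final lock after Week 108.
- Add a named Week 24 lock of the Efficacy Phase data, preceded by its own data review meeting at which per-protocol membership and single-visit exclusions are decided.
- Require the SAP, including the estimand definition and the handling of early, late and unscheduled lipid samples, to be final and dated before the Week 24 data cut and before any aggregate post-Baseline efficacy output is produced.
- Limit later changes to dated amendments covering the Safety Phase and follow-up analyses.
- In Sections 12.3 and 12.6, say that the lock meant for the Efficacy Phase analyses is the Week 24 lock.

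The cost is a few sentences, an earlier SAP sign-off and one additional data review meeting. No patient procedure, data item or sample-size figure changes.

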### **13.3.6 Data to be Recorded Directly into the Electronic Case Report Form**

The eCRF will serve as source document for the ethnic origin, which will only be recorded for the study.

## **13.4 Study and Site Closure**

Upon completion of the study or premature study (site) closure, the monitor and the investigator will be responsible for

- Return of all study data to Amryt Pharmaceuticals DAC
- Data clarification and/or resolution
- Accounting, reconciliation and return of used and unused study medication
- Review of study site records for completeness
- Return of all study specific equipment to Amryt Pharmaceuticals DAC

Amryt Pharmaceuticals DAC reserves the right to suspend or prematurely discontinue this study at either a single site or at all sites at any time for any reason. Amryt Pharmaceuticals DAC will inform the investigator(s), the IECs/IRBs, and the regulatory authorities if the study will be suspended or stopped prematurely.

### **13.5 Audits and Inspections**

Amryt Pharmaceuticals DAC or its designee may conduct a quality assurance audit of this study to evaluate compliance with the protocol and the principles of GCP. The investigator agrees to allow the auditor direct access to all relevant documents and to allocate his/her time and the time of his/her staff to the auditor to discuss findings and any relevant issues.

Regulatory agencies may conduct a regulatory inspection of this study. If a regulatory authority requests an inspection, the investigator must inform Amryt Pharmaceuticals DAC immediately about this request. The investigator agrees to allow the inspector(s) direct access to all relevant documents and to allocate his/her time and the time of his/her staff to the inspector(s) to discuss findings and any relevant issues.

## **14 LEGAL AND ETHICAL REQUIREMENTS**

This study will be conducted in accordance with the harmonised tripartite ICH Guidelines for GCP and all applicable laws and regulations, including the Declaration of Helsinki, June 1964, as modified by the 64th World Medical Association General Assembly, Fortaleza, Brazil, October 2013 (see Appendix 7 *Declaration of Helsinki*).

### **14.1 Regulatory Authority Approval**

Documents required for the application of this study will be submitted to the responsible competent authority according to the applicable country-specific laws and regulations. The study will not start until the competent authority authorises the study.

### **14.2 Independent Ethics Committee/Institutional Review Board**

This protocol, any amendments if applicable, any material provided to the patient (such as patient information, informed consent form and patient questionnaires) as well as additional documents, which may be required by national regulations and the IEC/IRB, will be submitted to the competent IEC/IRB for review and approval.

Written approval from the IEC/IRB must be obtained before starting the study, and must be documented in a letter specifying the date on which the IEC/IRB met and granted the approval. The IEC/IRB approval letter must identify all documents approved by listing the study number, study title, study sites/investigators, date and version of study protocol, date and version of patient information/informed consent form. A list of IEC/IRB members should be attached to the approval letter.

Any subsequent modifications made to the protocol or to any other documents that must be reviewed by the IEC/IRB must also be submitted to the IEC/IRB in accordance with local procedures and regulatory requirements.

### **14.3 Patient and Parent/Legal Guardian Information and Informed Consent**

In addition to information sheets and consent/assent forms for patients (according to applicable local regulations), parent/legal guardian information sheets and consent forms will be prepared.

The investigator will explain the aims, methods, objectives and potential risks and benefits of the study to the patient and the parent/legal guardian and will obtain written informed consent/assent from the patient (according to applicable local regulations) and written informed consent from the parent/legal guardian before he/she will initiate any study-specific procedure.

The patient and the parent/legal guardian will have sufficient time to ask and resolve any questions pertaining to participation in the study, and to consider study participation. In the

event that a patient is unable to read or will only be able to provide verbal informed consent, the parent/legal guardian may act on the patients' behalf.

The investigator will also explain to the patient and the parent/legal guardian that the patient will be free to refuse entering the study or to withdraw from it at any time for any reason. Neither the refusal to give consent nor the withdrawal of consent will result in discrimination of the patient, in particular regarding his/her subsequent medical treatment.

The patient (according to applicable local regulations) and the parent/legal guardian will be asked to review, sign, and date the informed consent form. He/she will receive a copy of the signed informed consent form, including the investigator's signature. The investigator will retain the original document.

The eCRF for this study will contain a section for documenting informed patient consent, which needs to be completed appropriately. The consent form will be reviewed and updated if the risk/benefit assessment changes or if amendments to the protocol affect the patients' participation in the study. All patients (including those already being treated) and their parents/legal guardians will be informed about the new information. Patients are only allowed to further participate in the study if they and their parents/legal guardians agree to sign the amended form, indicating that they reconsent to participate in the study.

#### **14.4 Data Protection**

Medical information about individual patients obtained in the course of this study is confidential and may not be disclosed to third parties, except authorised monitors, auditors or inspectors. Confidentiality will be ensured by the use of patient numbers for the identification of each patient; these patient numbers will also be used for patient data in the patient files and eCRFs. The investigator should keep a patient enrolment log showing codes, names and addresses and should maintain documents, e.g., patients' written consent forms, in strict confidence.

#### **14.5 Notification of Primary Care Physician**

The investigator should notify the patients' primary care physician of the patients' participation in the study, if applicable and agreed by the patient and his/her parent/legal guardian.

#### **14.6 Investigator Reporting Requirements**

The investigator will ensure that site study team members will promptly bring AEs/SAEs to his/her attention. He/she will report all AEs/SAEs as described in Section 11.4 *Documenting of Adverse Events and Serious Adverse Events* and Section 11.5 *Immediately Reportable Information*. The investigator will inform his/her IEC/IRB of any SAE in accordance with the local reporting requirements.

#### **14.7 Record Retention**

Upon closure of the study, the investigator/study site will maintain a copy of all study records in a safe and designated location at the study site in accordance with applicable regulatory requirements. Amryt Pharmaceuticals DAC will inform the investigator/study site of the time for retaining these records to comply with applicable regulatory requirements.

Essential documents as defined in the ICH E6 Guideline of GCP must be retained until

- 2 years after the last approval of a marketing application in an ICH region
- There are no pending or contemplated marketing applications in an ICH region
- 2 years will have elapsed since the formal discontinuation of clinical development of the investigational product
- Longer if required by the applicable regulatory requirement(s)/the sponsor

Unless other Union law (outside of the EU) requires archiving for a longer period, the sponsor and the investigator will archive the content of the clinical trial master file for at least 25 years after the completion or discontinuation of the study. The medical files of patients will be archived in accordance with local regulations.

## **15 PROTOCOL AMENDMENTS**

All protocol amendments must be submitted to the competent IECs/IRBs and Regulatory Agencies for information and/or approval in accordance with local requirements. If applicable, approval must be awaited before changes can be implemented, except for changes necessary to eliminate an immediate hazard to patients.

## **16 DISCLOSURE OF INFORMATION**

All data and records generated during the study except for patient medical records and all inventions discovered in the course of conducting the study, whether patentable or not, are the sole and exclusive property of Amryt Pharmaceuticals DAC.

The investigator and site study team members will keep strictly confidential any information provided by Amryt Pharmaceuticals DAC related to this study and all data and records generated in the course of conducting the study. They will not use the information, data or records for any other purpose than conducting the study without prior written approval of Amryt Pharmaceuticals DAC.

Amryt Pharmaceuticals DAC will prepare an integrated clinical study report in accordance with the harmonised tripartite ICH E3 Guideline '*Structure and Content of Clinical Study Reports*' after completion of the study.

